7.2.3 Multiple Imputation for Missingness of the Primary Outcome

The primary outcome, number of days of risky opioid use within the first 180 days since baseline, is measured by repeated monthly assessments. For each monthly assessment, participants will record the number of days of risky use within the previous 30 days. We consider two types of missing data for this outcome:

- *Missingness due to dropout*: patient participants may withdraw early from the study and miss all subsequent monthly measurements.
- *Intermittent missingness*: patient participants may miss one or more monthly surveys, or fail to complete the opioid items on the survey, while remaining enrolled in the study.

It was anticipated during the study design stage that up to 20% of participants may be missing data for the primary endpoint due to dropout and/or nonresponse. Exclusion of those participants with missing values could lead to underestimation of variance and biased estimated parameters. Multiple imputation (MI) will be performed for the primary analysis to account for missingness of the primary outcome variable. For the sake of best practice, if a patient participant misses the response values at baseline and in each of the monthly surveys for the risky opioid use questions for all 12 post-baseline collections, the patient participant will be excluded from multiple imputation since the analysis has little or no information to inform what those actual values might have been.

Multiple imputation consists of three steps:

1. Imputation step. An 'imputation' generally represents one set of plausible values for missing data – multiple imputation represents multiple sets of plausible values. When using multiple imputation, missing values are filled in to generate multiple completed datasets.
2. Completed-data analysis (estimation) step. The desired analysis is performed separately for each dataset that is generated during the imputation step.
3. Pooling step. The results obtained from each completed data analysis are combined into a single multiple imputation result.

Data for the primary outcome analysis is collected from the HLM survey. The analysis dataset includes monthly risky opioid use in Month 1, Month 2, Month 3, ..., Month 6 for the first 6 months post-enrollment, along with baseline risky opioid use, site, treatment, and PCP cluster.

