 - It is assumed that patient participants who drop out will have higher use after their dropout date than those who remain in the study, that is, that days of use after the withdrawal timepoint for dropouts in the treatment arm may more closely resemble that of controls than that of other treated patient participants. The values of missingness due to dropout might not retain the trend of prior observations since they are not exposed in the study environment due to various reasons, therefore the mechanism of missingness is assumed missing not at random (MNAR).

For the imputation of the primary outcome, two separate imputation procedures will be used to complete the imputation process for intermittent missingness and dropout. In the first step, the MI procedure statement uses the Markov Chain Monte Carlo (MCMC) method to impute the values of missing outcomes from intermittent missingness under the missing assumption of MAR. The variables specified in the mixed-effect regression model in Section 7.2.2, are included for imputation of primary outcome. The SAS code for imputing missing data from intermittent missingness is given below.

```
/* imputing the intermittent missingness with MAR assumption */
PROC MI DATA=datamiss nimpute=30 OUT=outimp1 SEED = 100623
min=. . 0 0 0 0 0 0
max=. . 30 30 30 30 30 30;
by treat;
mcmc impute=monotone;
VAR treat site baseline daysinmon1-daysinmon6;
RUN;
```

In this step, this MI procedure produces 30 imputed datasets by filling in the missing values from intermittent missingness with statement “impute=monotone”, and then produces the datasets as monotone missingness. The missing values due to intermittent missingness are imputed assuming that the intervention effect is still carried out while they remain enrolled in the study.

Next, MI procedure is to impute missing values from the dropouts under assumption of missing not at random (MNAR), which is a control-based pattern imputation assuming that after dropout, the unobserved values in the intervention group follow the path of observed values in control group. Based on this assumption, only the observed values in EUC group are used to derive the posterior distribution of the parameters from which the missing values in both EUC and STOP group are imputed. This approach is conservative as it tends to reduce the difference between STOP group and EUC group. The SAS code for imputing missing data from dropout is given below.

```

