14.0 ADDENDUM

14.1 Zero-Inflated Negative Binomial Model for the Primary Outcome

CTN-0101 is a prevention study, enrolling individuals who have risky opioid use but do not meet DSM-5 diagnostic criteria for a moderate or severe opioid use disorder (OUD). As such, it is anticipated that some participants may avoid all risky opioid use during the primary outcome measurement period. This is expected to result in an excess of zero-use days (i.e., zero-inflation) in the sample. In this case, the treatment effect may be in two forms: 1. Higher likelihood for people to have no risky opioid use; and 2. Lower days of use for people with non-zero days of risky opioid use.

To investigate this, as a post hoc analysis to the primary outcome analysis, a zero-inflated negative binomial (ZINB) model will be fit for the primary outcome data. The ZINB model accounts for excess zeros by assuming that they arise from a mixture of two processes: (1) participants who completely avoided risky opioid use during the treatment period, and (2) participants who did not completely avoid risky opioid use during the treatment period but may still have reported zero days of opioid use during this period. This model provides two estimates of the treatment effect: an odds ratio for “completely avoiding opioid use” and a rate ratio for the number of days of risky opioid use. The treatment effects of STOP from this model will be given as 1) an odds ratio, the

exponentiated estimate of the treatment effect from the logit model, along with a 95% confidence interval, and 2) a rate ratio, the exponentiated estimate of the treatment effect from the negative binomial model, along with a 95% confidence interval. Additionally, the overall treatment effect will be estimated using the shared parameter marginal ZINB (SPMZINB) model [14]. The treatment effect of STOP from this model will be given as a rate ratio, the exponentiated estimate of the treatment effect, along with a 95% confidence interval. Both models will be fit in SAS using Proc GENMOD (ZINB model) and Proc NL MIXED (SPMZINB model) and will use the multiply imputed primary outcome datasets. The results from these models will be used to explore the extent and impact of zero-inflation in the primary outcome for this study.

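### The ZINB zero part in SAP 14.1 uses imputed totals that can hardly ever be zero, so the zero share is understated; separately, the primary imputation code needs correcting

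*SAP*

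**What the plan says.** SAP 14.1, the only change listed for version 2.0 in SAP 15.0, expects some participants to avoid all risky use: "This is expected to result in an excess of zero-use days (i.e., zero-inflation) in the sample". It introduces its models with "To investigate this, as a post hoc analysis to the primary outcome analysis". The ZINB gives an odds ratio for complete avoidance and a rate ratio for days of use. A second model, the SPMZINB, gives one overall rate ratio. On purpose, 14.1 says: "The results from these models will be used to explore the extent and impact of zero-inflation in the primary outcome for this study". On data, the models are fitted in SAS "and will use the multiply imputed primary outcome datasets".

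Those datasets come from SAP 7.2.3, which anticipates that "up to 20% of participants may be missing data for the primary endpoint due to dropout and/or nonresponse". Step 1 fills intermittent gaps under missing at random, by arm, with `"mcmc impute=monotone"`. Step 2 fills months after dropout by monotone linear regression with a control-based model, in which "only the observed values in EUC group are used to derive the posterior distribution of the parameters". Both steps use the variable list `"VAR treat site baseline daysinmon1-daysinmon6"` with minimum and maximum lists, and neither prints a rounding option. SAP 7.1 defines the outcome as the sum of the six monthly values.

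**The concern.** A total built from six monthly values is zero only if all six are zero. If a filled-in month is a continuous draw, an abstainer who missed one survey becomes a user in all 30 datasets. The imputation then removes part of the feature that 14.1 was added to examine. What is at stake is the reported extent of zero-inflation and, if missingness differs between arms, the avoidance odds ratio, which could show an apparent benefit or harm created by missing surveys alone.

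The dropout assumption does not call for this. Imputing from EUC should still return some zeros if EUC contains abstainers, and gaps are assumed missing at random.

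Reading the same code also shows a bounds list that does not match its variable list, and a model call on the imputed data that differs from the one in SAP 7.2.2. These concern the primary analysis and are a separate item.

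**Working it through.** **Inputs.** From the documents: the six-month sum (SAP 7.1); up to 20% missing (SAP 7.2.3); user parameters of 20 against 14 days per 90, PCP variance 0.15, individual variance 0.25, and 60 PCPs with 5 patients (SAP 10.0). Assumed: zero shares, splits of missingness by arm, and, in the simulation, half the users light (1.5-3% of days) and missing participants half dropout, half gaps. The SAP states no zero share and no avoidance odds ratio, so there is no plan figure to reproduce on this point.

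**1. Zeros kept.** If draws are continuous and an out-of-range draw is drawn again rather than set to the bound (SAS was not run), an exact zero has probability 0. Then apparent zero share = true share × (1 − share with a missing month). With 30% zeros and 20% missing: 0.30 × 0.80 = 0.24. In an arm of 150, that is 36 zeros instead of 45.

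**2. Odds ratio for a zero total, STOP against EUC.**

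| True zeros EUC/STOP | Missing EUC/STOP | Zeros kept EUC/STOP | Odds ratio, true → apparent |
|---|---|---|---|
| 30%/40% | 20%/20% | 24.0%/32.0% | 1.56 → 1.49 |
| 30%/40% | 18%/22% | 24.6%/31.2% | 1.56 → 1.39 |
| 30%/40% | 15%/25% | 25.5%/30.0% | 1.56 → 1.25 |
| 30%/30% | 18%/22% | 24.6%/23.4% | 1.00 → 0.94 |
| 30%/30% | 15%/25% | 25.5%/22.5% | 1.00 → 0.85 |
| 30%/30% | 25%/15% | 22.5%/25.5% | 1.00 → 1.18 |

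First row: (0.32/0.68)/(0.24/0.76) = 1.49, against (0.40/0.60)/(0.30/0.70) = 1.56.

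**3. Simulation of the imputation.** In runs of 3,000 patients with about 20% missing a month, 0 of 74, 102, 174 and 210 true abstainers with an imputed month kept a zero total. Zero shares fell from 10.0%, 19.8%, 28.5% and 39.1% to 7.6%, 16.4%, 22.7% and 32.1%. A trial-sized simulation (200 replicates, 3 imputations each) with 30%/40% abstainers and 20% missing per arm gave a zero share of 35.6% in full data and 28.4% as planned, and an odds ratio of 1.54 and 1.49. With 15% missing in EUC and 25% in STOP the odds ratio went from 1.54 to 1.225. Fitted ZINB zero-part medians (60 replicates) went from 1.59 to 1.49 and from 1.59 to 1.16. The ratio of means, planned imputation against matching, was 0.648 against 0.641 (equal missingness) and 0.658 against 0.642 (15%/25%).

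**4. Would unprinted rounding help?** Little. In the 3,000-patient runs it restored 9/74, 23/102, 29/174 and 45/210 zeros, that is 12% to 23%. In the trial-sized simulation, 4.4% of those with a missing month had a zero total after rounding, against 35.7% in full data.

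**5. Bounds.** The variable list has 9 members: treatment, site, baseline and six months. Each bounds list has 8 entries: two blanks, then six limits. Read by position, 0-30 falls on baseline and Months 1-5, and Month 6 has no limit. In step 1 the `by treat` line might remove treatment from the count. Step 2 has treatment in both CLASS and VAR and no BY line, so the mismatch stands there. With Month 6 unbounded, simulation gave 12-22% of Month 6 draws negative and 0.4-0.7% of participants with a negative total.

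**6. Model calls side by side.** SAP 7.2.2 prints `METHOD=quad`, `solution` and `ddfm=bw`. The call on the imputed data in 7.2.3 prints none of the three. It reads `outmi`, although the last step writes `outimp2`; it saves `GPARMS`, while pooling reads `mixparms` with `CLASS visno`. Step 2 processes the stacked step 1 output with no BY `_imputation_` line.

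**The case against.** The strongest reply is that this is post hoc and small. With equal missingness the shift on the log scale is ln(1.556/1.490) = 0.043. At 150 per arm with 36 and 48 zeros, the standard error is √(1/36 + 1/114 + 1/48 + 1/102) = 0.26 ignoring clustering, so the shift is under 0.2 standard errors. The 20% is an upper figure; Protocol 10.9 lets a missed survey be completed with the next one, and Protocol 8.2.2 pays a bonus for consecutive completion. All of this stands for the odds ratio. It does not restore the zero share, which falls in proportion to missingness at any level.

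A second reply is that the planned imputation suits the SAP's own view of dropout. This is partly right. When STOP dropouts were simulated to resume use as EUC patients would, with 20% missing in each arm, the planned odds ratio was correct (1.49) and matching gave 1.55. The zero share was still understated (35.1% to 28.4%). With 15%/25% the true value was 1.47, planned 1.225 and matching 1.54.

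Third, no printed line builds the 180-day total, so rounding may happen there. It is possible but not stated, and it would recover few zeros.

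Fourth, the 7.2.2 code is called a template and its text states quadrature. That makes the option mismatch clerical, but the imputed-data call is the one that produces the primary result.

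**Conclusion.** The point holds for the zero part of the ZINB. As printed, the zero share is understated by about one fifth at 20% missing, and proportionately less at lower missingness. The odds ratio is nearly unaffected under equal missingness and can move in either direction otherwise. This rests on continuous draws that are redrawn when out of range, on no effective unprinted step, and on assumed zero shares and arm splits.

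Three stronger readings are not supported. A reader might infer that both post hoc models fail; only the ZINB zero part measures avoidance, and the effect on the SPMZINB rate ratio was not assessed. A reader might infer that the primary result is distorted; in simulation the ratio of means hardly changed. A reader might infer that the odds ratio is known to be biased against STOP; the documents give no missingness by arm, and reversing the split reverses the direction.

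The code mismatches in 7.2.3 are real on the page. Their effect in SAS is untested, and the effect of an unbounded Month 6 on the primary ratio is not quantified.

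**What to change.** **(a) SAP 14.1.** Report beside the imputed-data ZINB the observed zero share by arm, missingness by arm, and the complete-case zero-part odds ratio. SAP Tables 30 and 31 already plan missing-data patterns by arm. Fit the ZINB to datasets from an imputation that can return exact zeros, such as predictive mean matching or a count or zero-inflated imputation model. Keep missing at random by arm for gaps and EUC-based imputation for dropout.

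The cost is extra code and no new data. Section 14.1 would then use different datasets from the primary analysis, and matching needs enough EUC donors with no use. Matching and complete-case odds ratios may be about 4-6% too high if STOP dropouts resume use more than EUC patients with the same history (1.55 against 1.49; 1.54 against 1.47). The SAP should say so.

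**(b) SAP 7.2.3, as a separate item.** Give the minimum and maximum lists one entry per variable so that 0-30 applies to Months 1-6. Run step 2 by `_imputation_`. Put `METHOD=quad`, `ddfm=bw` and `solution` in the imputed-data model. Align `outimp2`/`outmi` and `GPARMS`/`mixparms`, and resolve `CLASS visno`. If the primary analysis has already been run, disclose the code actually used and report any corrected run alongside it rather than in its place.

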15.0 UPDATES TO THE STATISTICAL ANALYSIS PLAN

Table 4: SAP Revision History		
SAP Version	Date of Approval	Summary of Changes
1.0	02JUL2024	Initial Version
2.0	23MAY2025	Added Section 14 ADDENDUM for zero-inflated negative binomial post hoc analyses of the primary outcome

17.0 LIST OF PROPOSED TABLES, FIGURES, AND LISTINGS

The below listing contains the tables, listings, and figures which will be provided by the DSC.

Section	Title	Population
Participant Enrollment and Disposition: PCP Participants	Summary of Screening by Site	Screened
	Cluster Level Randomizations by Site and Treatment Arm	Randomized
	Individual Level Randomizations by Site and Treatment Arm	Randomized
	Summary of Disposition by Site	Randomized
	Summary of Disposition by Treatment Arm	Randomized
	Summary of Number of Patient Participants Enrolled per PCP Participant Cluster by Site	Randomized
	Summary of Number of Patient Participants Enrolled per PCP Participant Cluster by Treatment Arm	Randomized
	CONSORT Flow Diagram	Screened
Participant Characteristics at Baseline: PCP Participants	Summary of Baseline Characteristics by Site	Randomized
	Summary of Baseline Characteristics by Treatment Arm	Randomized
	Summary of Baseline Characteristics in Study Completers by Treatment Arm	Study Completers
Participant Enrollment and Disposition: Patient Participants	Summary of Prescreens by Site	Prescreened
	Summary of Screens by Site	Screened
	Summary of Prescreens, Screens, and Enrollments by Site	Prescreened
	Enrollments by Site and Treatment Arm	ITT
	Figure of Expected versus Actual Enrollments Overall	ITT
	Figure of Expected versus Actual Enrollments by Site	ITT
	Proposed and Actual Enrollments by Site	ITT
	Summary of Disposition by Site	ITT
	Summary of Disposition by Treatment Arm	ITT
	CONSORT Flow Diagram	Prescreened
Participant Characteristics at Baseline: Patient Participants	Summary of Baseline Characteristics by Site	ITT
	Summary of Baseline Characteristics by Treatment Arm	ITT
	Summary of Baseline Characteristics by Primary Outcome Availability and Treatment Arm	ITT
	Summary of Baseline Characteristics in Study Completers by Treatment Arm	Study Completers
Monthly Survey Completion: Patient Participants	Summary of Healthy Living Monthly Assessment Completion by Site	ITT
	Summary of Healthy Living Monthly Assessment Completion by Treatment Arm	ITT
Visit Attendance: Patient Participants	Summary of Attendance at Study Visits by Treatment Arm	ITT
	Summary of Missed Visits by Treatment Arm	ITT
	Summary of Primary Care Provider Interactions by Site	ITT

Section	Title	Population
STOP Intervention Exposure: Patient Participants	Summary of Nurse Care Manager Interactions by Site	ITT
	Summary of Telephone Health Coach Interactions by Site	ITT
Primary Outcome	Summary of Primary Outcome Availability by Treatment Arm in ITT Population	ITT
	Summary of Missing Risky Opioid Use Data Patterns by Treatment Arm in ITT Population	ITT
	Summary of Participants by Missing Risky Opioid Use Data Pattern and Treatment Arm in ITT Population	ITT
	Summary of Primary Outcome Analysis by Treatment Arm Using Multiple Imputation in ITT Population	ITT
Sensitivity Analyses of the Primary Outcome	Summary of Primary Outcome Analysis by Treatment Arm in Complete Case Population	Complete Case
	Summary of Primary Outcome Analysis by Treatment Arm Using Multiple Imputation Assuming Missing at Random in ITT Population	ITT
Supplemental Analyses of the Primary Outcome	Summary of Primary Outcome Analysis by Treatment Arm with Individual-level Covariate Adjustment in ITT Population	ITT
	Summary of Primary Outcome Analysis by Sex and Treatment Arm	ITT
	Summary of Primary Outcome Analysis by Age and Treatment Arm	ITT
	Summary of Primary Outcome Analysis by Race and Treatment Arm	ITT
	Summary of Primary Outcome Analysis by Ethnicity and Treatment Arm	ITT
	Summary of Primary Outcome Analysis in Per Protocol Population	Per Protocol
Supportive Analysis of the Primary Outcome	Summary Statistics of Risky Opioid Use by Treatment Arm	ITT
	Summary of Risky Opioid Use in Past 30 Days by Treatment Arm	ITT
	Summary of Risky Opioid Use in Past 90 Days by Treatment Arm	ITT
	Summary of Risky Opioid Use During Months 7-12 by Treatment Arm	ITT
Secondary Outcomes (Patient-level): Binge Alcohol use	Summary Statistics of Binge Alcohol Use by Treatment Arm	ITT
	Summary of Binge Alcohol Use in Past 30 Days by Treatment Arm	ITT
	Summary of Binge Alcohol Use in Past 90 Days by Treatment Arm	ITT
	Summary of Binge Alcohol Use in Past 180 Days by Treatment Arm	ITT
Secondary Outcomes (Patient-)	Summary Statistics of Benzodiazepine Use by Treatment Arm	ITT
	Summary of Benzodiazepine Use in Past 30 Days by Treatment Arm	ITT

Section	Title	Population
level): Benzodiazepine use	Summary of Benzodiazepine Use in Past 90 Days by Treatment Arm	ITT
	Summary of Benzodiazepine Use in Past 180 Days by Treatment Arm	ITT
Secondary Outcomes (Patient- level): Stimulant Drug Use	Summary Statistics of Stimulant Drug Use by Treatment Arm	ITT
	Summary of Stimulant Drug Use in Past 30 Days by Treatment Arm	ITT
	Summary of Stimulant Drug Use in Past 90 Days by Treatment Arm	ITT
	Summary of Stimulant Drug Use in Past 180 Days by Treatment Arm	ITT
Secondary Outcomes (Patient- level): Marijuana Use	Summary Statistics of Marijuana Use by Treatment Arm	ITT
	Summary of Marijuana Use in Past 30 Days by Treatment Arm	ITT
	Summary of Marijuana Use in Past 90 Days by Treatment Arm	ITT
	Summary of Marijuana Use in Past 180 Days by Treatment Arm	ITT
Secondary Outcomes (Patient- level): Other Drug use	Summary Statistics of Other Drug Use in Past 30 Days by Treatment Arm	ITT
Secondary Outcomes (Patient- level): Urine Screen Test Results	Summary of Positive UDS Results by Visit and Treatment Arm	ITT
	Summary of Positive UDS Results by Visit, Prescription for Opioids, and Treatment Arm	ITT
Safety: Patient Participants	Summary of Non-fatal Drug or Alcohol Overdoses in the Past 6 Months by Treatment Arm	Safety
	Summary of Suicide Risk by Treatment Arm	Safety
	Summary of Hospitalizations by Treatment Arm	Safety
	Summary of Emergency Department Visits by Treatment Arm	Safety
	Listing of Non-fatal Drug or Alcohol Overdoses by Treatment Arm	Safety
	Listing of Suicide Risk by Treatment Arm	Safety
	Listing of Hospitalizations by Treatment Arm	Safety
	Listing of ED Visits by Treatment Arm	Safety
	Listing of Death by Treatment Arm	Safety
	Death Narratives	Safety
Data Quality	Summary of Data Audits	N/A
Protocol Deviations	Summary of Protocol Deviations by Site	N/A
	Listing of Protocol Deviations	N/A

18.0 APPENDICES

18.1 Proposed Tables, Listings, and Figures

1 Participant Enrollment and Disposition: PCP Participants

Table 1: Summary of Screening by Site
PCP Participants

	Chase-Breton Health Center	Dartmouth- Hitchcock	Annville Family Medicine	University of Utah	The Ohio State University	Total
Number of potentially eligible provider participants	N					
Number not approached for screening ¹	N (X.X%)					
Criterion resulting in ineligibility for screening ²						
Not providing care to approximately 4 or more adult patients receiving chronic opioid treatment and/or have risky opioid use	N (X.X%)					
Total patient volume not approximately 40 or more patients per week						
Number approached for screening ¹	N (X.X%)					
Number that did not take screening survey ³	N (X.X%)					
Number screened ³	N (X.X%)					
Number of eligible screens ⁴	N (X.X%)					
Number of ineligible screens ⁴	N (X.X%)					
Criterion resulting in ineligibility ⁵						
Not a licensed medical professional (MD, DO, PA, NP)	N (X.X%)					
Not willing to be randomized to either of the study conditions						
Plans to leave the study clinic within the next 24 months						
Plans to change their schedule so they no longer have the required patient volume						

Table 1: Summary of Screening by Site
PCP Participants

	Chase-Breton Health Center	Dartmouth -Hitchcock	Annville Family Medicine	University of Utah	The Ohio State University	Total
Number of provider participants eligible but not randomized ⁶	N (X.X%)					
Reasons for not being randomized ⁷						
No longer interested in participating in the study	N (X.X%)					
Judgment of site/research staff						
Unable to contact						
Time commitment						
COVID-19: Illness						
COVID-19: Public health measures						
COVID-19: Other						
Other						
Number eligible and randomized ⁶	N (X.X%)					

1 Percentages are calculated based on the denominator of the number of potentially eligible provider participants.

2 Percentages are calculated based on the denominator of the number of providers not approached for screening.

3 Percentages are calculated based on the denominator of the number of providers approached for screening.

4 Percentages are calculated based on the denominator of the number of providers screened.

5 Percentages are calculated based on the denominator of the number of ineligible screens and may sum to greater than 100% if multiple eligibility criteria are not met for potential provider participants.

6 Percentages are calculated based on the denominator of the number of eligible screens.

7 Percentages are calculated based on the denominator of the number of provider participants eligible but not randomized.

Table 2: Cluster Level Randomizations by Site and Treatment Arm			
PCP Participants			
Site	Treatment Arm		Total (N=)
	EUC (N=)	STOP (N=)	
Chase-Brexton Health Center	N (X.X%)	N (X.X%)	N
Dartmouth-Hitchcock			
Annville Family Medicine			
University of Utah			
The Ohio State University			
Total			

This table presents cluster level randomizations, where a cluster consists of providers that work in teams. All sites except Dartmouth-Hitchcock work as individual providers, and therefore in those four sites, a cluster is equivalent to an individual provider.

Table 3: Individual Level Randomizations by Site and Treatment Arm			
PCP Participants			
Site	Treatment Arm		Total (N=)
	EUC (N=)	STOP (N=)	
Chase-Brexton Health Center	N (X.X%)	N (X.X%)	N
Dartmouth-Hitchcock			
Annville Family Medicine			
University of Utah			
The Ohio State University			
Total			

This table presents individual provider level randomizations. The actual unit of randomization is a cluster, where a cluster consists of providers that work in teams. All sites except Dartmouth-Hitchcock work as individual providers, and therefore in those four sites, a cluster is equivalent to an individual provider.

**Table 4: Summary of Disposition by Site
PCP Participants**

	Chase-Brexton Health Center	Dartmouth- Hitchcock	Annville Family Medicine	University of Utah	The Ohio State University	Total
Number of provider participants randomized	N					
Number of study completers ¹	N (X.X%)					
Number of early study terminations ²	N (X.X%)					
Reason for early study termination						
No longer interested in participating in the study	N (X.X%)					
Judgement of site/research staff						
Plans to leave the practice						
Reduced patient panel						
Other						

¹ A provider participant is a study completer if there is no early withdrawal from the study documented on the Provider Eligibility Review eCRF (PCP).

² A provider participant is an early study termination if early withdrawal (and reason for withdrawal) is completed on the PCP eCRF

Table 5: Summary of Disposition by Treatment Arm			
PCP Participants			
	Treatment Arm		Total (N=)
	EUC (N=)	STOP (N=)	
Repeat of Table 4 with Treatment Arm for columns			

Note: All clusters with >1 PCP completed the trial, because at least one PCP remained active in the trial.

Table 6: Summary of Number of Patient Participants Enrolled per PCP Participant Cluster by Site

[figure not shown]
	Chase-Brexton Health Center	Dartmouth -Hitchcock	Anville Family Medicine	University of Utah	The Ohio State University	Total
Number of provider participants randomized	N					
Number of provider participant clusters randomized	N					
Number of patient participants enrolled	N					
Number of provider participant clusters with at least one patient participant enrolled	N (X.X%)					
Number of patient participants per provider participant cluster ¹						
N	N					
Mean	X.X					
SD	X.XX					
Min	X.X					
25th Percentile	X.X					
Median	X.X					
75th Percentile	X.X					
Max	X.X					
Number of provider participant clusters						
0 patient participants	N (X.X%)					
1 patient participant						
2 patient participants						
3 patient participants						
4 patient participants						
5 patient participants						
...						
X patient participants						

¹ For provider participant clusters that have at least one patient participant enrolled.

Table 7: Summary of Number of Patient Participants Enrolled per PCP Participant Cluster by Treatment Arm

	Treatment Arm		Total (N=)
	EUC (N=)	STOP (N=)	
Repeat of Table 6 with Treatment Arm for columns			

**Figure 1: CONSORT Flow Diagram
PCP Participants**

¹ Potential PCP participants may be ineligible for multiple reasons.

² The unit of randomization is a cluster, or PCPs that work on a team. Dartmouth-Hitchcock is the only site whose PCPs practice in teams. Dartmouth-Hitchcock randomized x clusters comprising x individual PCPs.

2 Participant Characteristics at Baseline: PCP Participants

Table 8: Summary of Baseline Characteristics by Site

PCP Participants

	Chase-Brexton Health Center (N=)	Dartmouth-Hitchcock (N=)	Annville Family Medicine (N=)	University of Utah (N=)	The Ohio State University (N=)	Total (N=)
Gender						
Missing	N (X.X%)					
Male						
Female						
Transgender						
Nonbinary						
Other						
Age in years (Mean (SD))	X.X (X.XX)					
Age in years						
Missing	N (X.X%)					
< 18						
18 - < 25						
25 - < 35						
35 - < 45						
45 - < 55						
55 - < 65						
65 - < 75						
75+						
Ethnicity						
Missing	N (X.X%)					
Not Hispanic or Latino						
Hispanic or Latino						
Refused to answer						
Race						
Missing	N (X.X%)					
American Indian or Alaska Native						
Asian						
Black or African American						
Native Hawaiian or Pacific Islander						

Table 8: Summary of Baseline Characteristics by Site

PCP Participants

	Chase-Brexton Health Center (N=)	Dartmouth-Hitchcock (N=)	Annville Family Medicine (N=)	University of Utah (N=)	The Ohio State University (N=)	Total (N=)
White						
Other						
Multiracial						
Don't know						
Refused to answer						
Medical Profession						
Missing	N (X.X%)					
Physician (MD/DO)						
Physician Assistant (PA)						
Nurse-Practitioner (NP)						

Table 9: Summary of Baseline Characteristics by Treatment Arm			
PCP Participants			
	Treatment Arm		Total (N=)
	EUC (N=)	STOP (N=)	
Repeat of Table 8 with Treatment Arm for columns			

Table 10: Summary of Baseline Characteristics in Study Completers by Treatment Arm
PCP Participants

	Treatment Arm		Total (N=)
	EUC (N=)	STOP (N=)	
Repeat of Table 9 for Study Completers			

3 Participant Enrollment and Disposition: Patient Participants

Table 11: Summary of Prescreens by Site

Patient Participants					
	Chase-Breton Health Center	Dartmouth-Hitchcock	Annville Family Medicine	University of Utah	The Ohio State University
Number of started prescreening attempts	N				
Number of completed attempts	N (X.X%)				
Number of prescreen eligible attempts	N (X.X%)				
Number of prescreen eligible patients ¹	N				
Number of ineligible prescreen attempts	N (X.X%)				
Criterion resulting in ineligibility ²					
≥18 years old	N (X.X%)				
Risky opioid use in past 90 days					

¹ Patients may take the prescreen survey multiple times. This is the number of unique IDs entered across all eligible prescreen record attempts.

² Percentages are calculated based on the denominator of the number of ineligible prescreens and may not sum to 100% if multiple eligibility criteria are not met for potential participants.

Table 12: Summary of Screens by Site
Patient Participants

	Chase-Breton Health Center	Dartmouth-Hitchcock	Annville Family Medicine	University of Utah	The Ohio State University	Total
Number screened	N					
Number of eligible screens	N (XX%)					
Number of ineligible screens	N (XX %)					
Criterion resulting in ineligibility ¹						
Inclusion Criteria						
PCP enrolled in study	N (XX%)					
Age 18 years or older at time of prescreening						
Proficient in spoken and written English						
Risky opioid use in the past 90 days from the date of prescreening						
Access to phone that can receive text messages and access to internet						
Able to provide sufficient contact information						
Willing and able to provide informed consent						
Exclusion Criteria						
Moderate to severe OUD	N (XX%)					
Received MOUD or engaged in opioid treatment program in past 30 days						
Receiving opioids for end of life care						
Pregnancy						
In jail, prison, or have pending legal action that could prevent participation in study activities						
Plan to leave the area or the clinical practice within the next 12 months						

Table 12: Summary of Screens by Site
Patient Participants

	Chase-Breton Health Center	Dartmouth- Hitchcock	Annville Family Medicine	University of Utah	The Ohio State University	Total
Other factors that may cause harm or increased risk or preclude adherence to study						
Number of participants eligible but not enrolled	N (X.X%)					
Reasons for not being enrolled ²						
No longer interested in participating in the study	N (X.X%)					
Judgment of site/research staff						
Unable to contact						
Time commitment						
COVID-19: Illness						
COVID-19: Public health measures						
COVID-19: Other						
Other						

¹ Percentages are calculated based on the denominator of the number of ineligible screens and may sum to greater than 100% if multiple eligibility criteria are not met for potential participants.

² Percentages are calculated based on the denominator of the number of participants eligible but not enrolled.

Table 13: Summary of Prescreens, Screens, and Enrollments by Site

Site	Patient Participants					Percent of Screens Enrolled
	Number of Completed Prescreen Attempts ¹	Number of Screens	Percent of Eligible Prescreens Screened	Number of Screen Fails	Percent of Screens Who Screen Fail	
Chase-Brexton Health Center	N	N	X.X%	N	X.X%	N
Dartmouth-Hitchcock						
Annville Family Medicine						
University of Utah						
The Ohio State University						
Total						

[figure not shown]
¹ Patients may prescreen multiple times and therefore be counted multiple times in this number.

Table 14: Enrollments by Site and Treatment Arm

Patient Participants

Site	Treatment Arm		Total (N=)
	EUC (N=)	STOP (N=)	
Chase-Brexton Health Center	N (X.X%)	N (X.X%)	N
Dartmouth-Hitchcock			
Annville Family Medicine			
University of Utah			
The Ohio State University			
Total			

Figure 2: Figure of Expected versus Actual Enrollments Overall
Patient Participants

Example figure provided.

**Figure 3: Figure of Expected versus Actual Enrollments by Site
Patient Participants**

[figure not shown]

Table 15: Proposed and Actual Enrollments by Site

Patient Participants

Site	Proposed Enrollments¹	Date Site Opened for Enrollment	Date of First Enrollment	Actual Enrollments	Actual/Proposed (%)	Date of Last Enrollment
Chase-Breton Health Center	N	mm/dd/yyyy	mm/dd/yyyy	N	X.X%	mm/dd/yyyy
Dartmouth-Hitchcock						
Annville Family Medicine						
University of Utah						
The Ohio State University						
Total						

¹ Proposed Enrollment = proposed number of enrollments per site based on the total sample size N.

**Table 16: Summary of Disposition by Site
Patient Participants**

[figure not shown]
	Chase-Breton Health Center	Dartmouth- Hitchcock	Annville Family Medicine	University of Utah	The Ohio State University	Total
Number of patient participants enrolled	N					
Number of study completers ¹	N (X.X%)					
Number of early study terminations ²	N (X.X%)					
Reason for early study termination						
Participant stopped participation due to practical problems (e.g. no childcare or transportation)	N (X.X%)					
Participant incarcerated						
Participant withdrew consent/assent						
Participant deceased						
Participant terminated for administrative issues						
Participant terminated due to pressure or advice from outsiders						
Participant in hospital, in-patient, or residential treatment (not for substance abuse treatment)						
Clinical deterioration: new onset of psychiatric or medical condition						
Participant in detox, residential, or intensive outpatient treatment for substance abuse treatment						
Participant refused, non-specific						
Unable to contact participant						
Participant terminated due to COVID-19: Illness						
Participant terminated due to COVID-19: Public health measures						
Participant terminated due to COVID-19: Other						
Participant terminated for other reason						

¹ A participant is a study completer if they have a completed Study Completion (STC) form indicating they have completed their last study activity.

² A participant is an early study termination if they have a completed STC form indicating they did not complete their last study activity.

Table 17: Summary of Disposition by Treatment Arm			
Patient Participants			
	Treatment Arm		Total (N=)
	EUC (N=)	STOP (N=)	
Repeat of Table 16 with Treatment Arm for columns			

Figure 4: CONSORT Flow Diagram
Patient Participants

¹ Potential patient participants may prescreen multiple times and therefore may be counted multiple times in this number.

